## B. Research question(s)

Research questions in this study are framed by a descriptive evaluation design that will be used to measure the extent to which participation in the FRAMEWorks Program is positively associated with improved attitudes and behaviors among low-income adults in the Houston, TX area. Research questions will focus on whether attitudes and behaviors related to parenting and partner relationships, and financial and job readiness behaviors change after participation in the program. Changes will be assessed between outcomes at program enrollment before primary workshops begin using entrance surveys and outcomes one year after program enrollment using the 1-year follow-up survey. The sample for the primary analysis includes all program participants who consent to be in the study, regardless of program format (e.g., virtual, in person, weekly workshops, weekend retreat). Implementation analyses seek to determine how many curriculum hours the program is offering versus how many curriculum hours participants are completing. Exploratory secondary analyses will investigate to what extent changes in outcomes differ between participants who receive the curriculum virtually vs. in person.

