### Ensuring and monitoring high quality data collection

This evaluation will utilize the nFORM and OLLE entrance surveys at enrollment and the OLLE 1-year follow-up surveys collected one year after enrollment. The data collection methods for these time points differ, as shown in Table 11 above and as discussed further in Table 12 below.

All program staff and evaluation staff will undergo a rigorous set of trainings to prepare for the evaluation. All staff receive an overview and introductory training to present the goals and objectives of the evaluation effort and its importance to the overall project. Next, all staff receive training on human subject protection and are required to pass a certification test on the subject matter. All staff will also receive a detailed training on the evaluation, including the

evaluation tools, timing and data collection process, and the role and importance of randomization of participants.

In addition, the data manager and the primary local evaluation staff will undergo a rigorous training process to better understand the context of HMRP research, training on data collection procedures they will be responsible for, and training on the nFORM system and use of nFORM data in a CQI process. MER is creating networks of CQI data managers and Evaluation Project Managers across the 12 projects that we are evaluating so that all staff have access to experienced data managers and evaluation staff who have done this work previously. This training takes the form of weekly training sessions that are currently underway.

Members of the CQI team will also receive specific training on the MER CQI process that has been developed prior to the launch of data collection or program services. As described elsewhere, MER is assisting the program staff in implementing a robust CQI process that will focus on retention as one of the primary areas of program improvement, and as such, we are anticipating relatively modest levels of attrition for this data collection.

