**Table 12: Tracking participants and reducing attrition**

For each wave of data collection listed in IIIA.2, what is your estimated response rate?	Entrance	100% - done at the time of enrollment
	Follow-Up	70% - estimated 1 year follow-up rate

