Step 1: Index scores will be compared between a participant's pre-survey and post-survey responses, and again between a participant's pre-survey and follow-up survey responses. Paired statistical tests will be used to determine if changes in outcomes between waves of data collection are significant ($p < 0.05$). The primary change of interest in this study is the difference between pre-survey responses and follow-up survey responses to see if changes persist long after program participation.

Step 2: To further explore how individual characteristics (e.g., gender), programmatic differences (e.g., virtual compared to in-person workshop delivery; weekly compared to weekend schedule format), and program dosage (e.g., number of primary hours received) may interact with program participation to create change in the outcomes of interest, a secondary analysis will be done using regression modeling. The data will be examined before analysis to determine if linear regression is appropriate. Statistical significance will be measured at the $p < 0.05$ level. The independent variables for this analysis will be a dosage measure quantifying the number of primary programming hours received and dummy variables for delivery method. Self-reported demographic characteristics will be taken from the nFORM Applicant Characteristics Survey (ACS) to be included as co-variates in the model. This will be an exploratory analysis and is not attempting to make a causal inference about the impact of program dosage or delivery method.

IRB/protection of human subjects

MER has received Institutional Review Board (IRB) approval from Solutions IRB to conduct this descriptive evaluation.

Solutions IRB, a private commercial Association for the Accreditation of Human Research Protection Programs Inc. (AAHRPP) fully accredited Institutional Review Board, will ensure that this study is approved before any research activities take place. MER has had 14 research studies approved by Solutions IRB over the past four years, has completed over 15 annual check-in reports, and has submitted timely amendments when changes to studies needed to take effect.

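### The stated primary sample is everyone who consents, but the paired one-year test can use only the roughly 70% expected to return a follow-up survey, and the SAP gives no method for the rest

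*SAP*

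**What the plan says.** Protocol section I.B sets the sample: "The sample for the primary analysis includes all program participants who consent to be in the study, regardless of program format". Protocol Table 3 labels R1 to R6 confirmatory, with pre-intervention scores as the only comparison.

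SAP section IV.A, Step 1, compares index scores within person at entrance and exit, and "again between a participant's pre-survey and follow-up survey responses". It then fixes the priority: "The primary change of interest in this study is the difference between pre-survey responses and follow-up survey responses". The method is: "Paired statistical tests will be used to determine if changes in outcomes between waves of data collection are significant", at p < 0.05.

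Protocol Table 12 gives the expected response as "100% - done at the time of enrollment" for entrance and "70% - estimated 1 year follow-up rate" for follow-up. Under the heading on high-quality data collection, the protocol says "we are anticipating relatively modest levels of attrition for this data collection".

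The SAP analysis section describes no imputation, weighting, model for incomplete pairs, comparison of responders with nonresponders, or missing-data sensitivity analysis. The measures the documents do contain are preventive: a $50 follow-up incentive (Protocol Table 7), a contact window from 60 days before to 30 days after the one-year date (Protocol Table 10), and quality-improvement work on retention.

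**The concern.** The sample definition and the test do not describe the same people. A participant with an entrance survey but no one-year survey belongs to the stated primary sample, yet contributes nothing to the primary test. The SAP does not use the words complete cases, but that is what a paired test gives when no other rule is stated. The regression mentioned at the start of section IV.A does not help: a model for the follow-up or change score loses the same people unless a missing-data method is added.

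What is at stake is who the confirmatory statements are about. R1 to R6 are worded as change among participants. If responders and nonresponders changed differently, a responders-only figure would be reported as though it held for everyone who enrolled. There is no comparison arm in which similar attrition might offset the difference.

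**Working it through.** **Inputs from the documents.** Entrance response 100% and one-year response r = 0.70 (Protocol Table 12); paired test on the entrance-to-one-year change (SAP IV.A, Step 1).

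**Inputs not in the documents.** The supplied text gives no effect size and no sample size. All SD figures and N values below are assumptions, in units of the SD of individual change.

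**Step 1: share excluded.** 1 − 0.70 = 0.30. This applies to the one-year contrast only; no exit-survey response rate is given. Item nonresponse, or items that do not apply to a participant, could raise the loss for some outcomes, but the documents give no figure.

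**Step 2: bias.** Let dR be the mean change in responders and dN the mean change in nonresponders.

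- All-consenter change = 0.70 × dR + 0.30 × dN
- Paired-test estimate = dR
- Bias = dR − (0.70 × dR + 0.30 × dN) = 0.30 × (dR − dN)

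A gap of 0.1, 0.2 or 0.3 SD therefore gives a bias of 0.03, 0.06 or 0.09 SD.

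**Step 3: illustration with dR = 0.20 SD.**

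- dN = 0.30: 0.14 + 0.09 = 0.23; the paired test understates, 0.20 / 0.23 = 0.87 (13% too low)
- dN = 0.20: 0.14 + 0.06 = 0.20; no bias
- dN = 0.10: 0.14 + 0.03 = 0.17; 0.20 / 0.17 = 1.18 (18% too high)
- dN = 0: 0.14 + 0 = 0.14; 0.20 / 0.14 = 1.43 (43% too high)
- dN = −0.20: 0.14 − 0.06 = 0.08; 0.20 / 0.08 = 2.5 (2.5-fold)

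**Step 4: when the all-consenter change reaches zero.** 0.70 × dR + 0.30 × dN = 0 gives dN = −(0.70 / 0.30) × dR = −2.33 × dR. Nonresponders would have to worsen by 2.33 times the responders' gain.

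**Step 5: effect on the test.** Suppose the all-consenter change is zero and responders did better than nonresponders by 0.2 SD, so b = 0.06. A two-sided 5% test (sidedness is not stated in the SAP) rejects with probability Φ(b√(0.7N) − 1.96) + Φ(−b√(0.7N) − 1.96). For assumed enrolled N of 200, 500, 1000 and 2000 this is about 11%, 20%, 36% and 61%. Enrolling more people does not reduce the bias; it makes the test more certain of the biased value.

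**Scale.** R5 and R6 use yes/no items (Protocol Table 9), so SD units do not describe them. The formula in Step 2 holds for them with dR and dN as changes in the proportion answering yes.

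**The case against.** Several points on the other side have weight.

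- **The direction is unknown.** A reader might infer that those lost are the low attenders or people in unstable circumstances, and hence that the paired test exaggerates benefit. The documents do not support this. The protocol lists homelessness and partner violence as background on the county; nothing describes nonresponders. The protocol does link its expected attrition to retention work, and SAP Step 2 allows that dosage may relate to change. That makes informative loss plausible but does not establish its direction. This objection stands.
- **The sizes are assumed.** There is no effect size or N in the text to anchor them. This stands too.
- **The sign need not change.** In every illustration in Step 3 the all-consenter change remains positive. A reader who infers that the study's conclusion would reverse goes beyond the evidence; see Step 4.
- **The sample sentence is mainly about format.** It says nobody is excluded for choosing virtual or weekend delivery, and does not set out to deal with incomplete pairs. That softens the conflict, but the sentence still names all consenters as the primary sample, and no other text defines the analysed set.
- **The study calls itself descriptive.** That lowers the severity. It does not remove the need to say whom the figures describe, because R1 to R6 are labelled confirmatory.
- **Text may be missing.** The supplied protocol stops at Table 12, so a rule elsewhere cannot be excluded. The SAP analysis section, where such a rule belongs, has none.
- **Imputing every outcome for every consenter would be ill-defined.** Eligibility in Protocol section II.C does not require a partner, so partner items may not apply to some participants. This limits the remedy and is built into the fix.

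**Conclusion.** The point holds in a limited form. Under the plan as written, the primary one-year result describes responders, about 70% of the stated primary sample, and no method covers the other 30%. The bias against the all-consenter change is 0.30 × (responder change minus nonresponder change). It may be zero, favourable or unfavourable, and the documents do not say which. The 30% follows from the protocol's own estimate; exclusion follows from how a paired test works; the SD illustrations are assumptions.

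A reader might also infer that exit scores are available to recover the missing information. That is not secure. The SAP uses exit surveys, but Protocol section III.C describes two time points for evaluation data, and Protocol Table 10 lists only entrance and one year.

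This should be fixed, but it does not by itself invalidate a descriptive study.

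**What to change.** 1. **Define the analysed set for each outcome**: all consented participants with an applicable entrance value. Partner items, for example, would be analysed only for those to whom they apply.
2. **Estimate the entrance-to-one-year change in that set** by multiple imputation, or by a likelihood-based repeated-measures model with the same predictors: entrance score, Applicant Characteristics Survey variables, delivery format and hours attended. Average the estimated change over the whole set. Use a binary-outcome model for the yes/no items in R5 and R6.
3. **Reconcile the SAP and protocol on exit surveys.** Add exit scores as predictors only if they are collected.
4. **Report the complete-pairs test alongside**, with a comparison of responders and nonresponders at entrance.
5. **Add a delta-shift sensitivity analysis**: shift the imputed one-year values in steps and report where each conclusion changes.
6. **If only complete pairs are analysed**, say so in both documents and limit the conclusions to one-year responders.

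The cost is SAP wording and modest programming. The entrance surveys, applicant characteristics and hours are already part of the planned data, and both databases carry the same client ID (SAP Table VC.2). The downside is reliance on a missing-at-random assumption, which the data cannot confirm; the delta-shift analysis is there to show how much depends on it.

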**Table 2: Research questions by type (implementation or outcome)**

No	Research Question	Implementation or Outcome?
I1	To what extent is the SSHF curriculum offered to and received by program participants?	Implementation
R1	How did parenting behavior outcomes change from program enrollment to 1 year after enrollment?	Outcome
R2	How did parenting attitude outcomes change from program enrollment to 1 year after enrollment?	Outcome
R3	How did partner relationship behavior outcomes change from program enrollment to 1 year after enrollment?	Outcome
R4	How did partner relationship attitude outcomes change from program enrollment to 1 year after enrollment?	Outcome

R5	How did financial readiness behavior outcomes change from program enrollment to 1 year after enrollment?	Outcome
R6	How did job readiness behavior outcomes change from program enrollment to 1 year after enrollment?	Outcome
R7	Do the change in outcomes differ between those selecting in-person or virtual groups?	Exploratory Outcome

Table 3 below summarizes key aspects of the research questions that are used to measure changes in participant outcomes after participation in the FRAMEWorks Program. For each outcome research question, there is a summary of the intervention, target population, comparison group, changes expected (the outcome), and whether the outcome is confirmatory or exploratory. As a secondary exploratory analysis, we will explore whether any differences in outcomes exist between those participants who receive the curriculum virtually vs. those who receive the curriculum in-person.

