AVANCE Houston FRAMEWorks Program Evaluation

Statistical Analysis Plan

2/6/2024

Clinicaltrials.gov ID:
NCT05261802

IV. Data Analysis

A. Data analysis

The local evaluators will run linear or logistic regression analyses to assess changes in participant outcomes after FRAMEWorks Program participation. Survey items will be explored individually and as part of constructs (e.g., parenting behaviors) that have been validated by confirmatory factor analysis. Relevant co-variables will be included in the models as controls. The evaluation team will continue to work with the program's ETAP to refine analytical methods.

To answer the ancillary question of potential differences between participants who participate virtually vs. in person, the local evaluators also plan to conduct an exploratory analysis of the moderating effect of delivery format.

Data analysis

Overview: The primary analysis for this descriptive study is to assess changes in outcomes presented in Table 2 after participation in the FRAMEWorks Program primary services. Changes in attitudes and behaviors are assessed by comparing participant responses on the OLLE and nFORM Healthy Marriage Adult Program Survey pre-surveys to participant responses on program exit surveys (OLLE and nFORM) and the OLLE 1-year follow-up survey.

Analysis begins by creating indices for constructs that will serve as the dependent variables. Constructs comprise the relevant behavioral or attitudinal survey items on the nFORM and OLLE surveys. All constructs have been confirmed with psychometric evidence derived from confirmatory factor analysis (CFA) or have already been supported by evidence of reliability and validity. Indices will be created by adding together the response codes for each of the scaled items within a given construct.

In addition to changes in the outcomes outlined above, exploratory analyses of differences in program format (weekly workshops compared to weekend retreat), virtual vs in-person, gender, and dosage are possible.

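### Step 2 enters hours received beside delivery format, so its format coefficient is a difference at equal hours and not the overall difference in change that R7 asks about; its dependent variable is also undefined

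*SAP*

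**What the plan says.** Protocol section I.B, Table 2, words R7 as: "Do the change in outcomes differ between those selecting in-person or virtual groups". Tables 2 and 3 label it exploratory. Under section II.A, participants choose their own format.

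SAP section IV.A promises, for the virtual versus in-person question, "an exploratory analysis of the moderating effect of delivery format". The only regression then described is Step 2, which names virtual versus in-person delivery as one of its subjects. It gives as its independent variables "a dosage measure quantifying the number of primary programming hours received and dummy variables for delivery method". On covariates it adds: "Self-reported demographic characteristics will be taken from the nFORM Applicant Characteristics Survey (ACS) to be included as co-variates in the model". The opening of IV.A has a broader line: "Relevant co-variables will be included in the models as controls". No model without hours is given for R7.

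Two statements bear on the dependent variable. The SAP overview says: "Analysis begins by creating indices for constructs that will serve as the dependent variables", without naming a wave. Step 2 speaks of factors that "may interact with program participation to create change in the outcomes of interest". Step 2 is declared exploratory and disclaims causal inference about dosage or delivery method.

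**The concern.** Format is settled at the start and hours accumulate afterwards. The Protocol's Background says people weigh childcare, travel, work schedules and location when choosing a format, and these could plausibly affect attendance too. If mean hours differ between virtual and in-person participants, a model holding hours fixed compares people who attended equally. R7 asks something else: how the two groups, as they actually attended, differ in change. The study could report no format difference when one exists, or a difference of the opposite sign, and pass that on for planning future cohorts, which is the use Protocol Table 1 gives for R7.

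The undefined dependent variable is a second gap. Because format is self-selected, entrance scores may differ between the groups. Whether that distorts the R7 answer depends on whether Step 2 models a change or a 1-year level.

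**Working it through.** The documents give no sample size, power or effect for R7, so there is no plan figure to reproduce. The check is what the format coefficient estimates under each candidate model. Each formula below was confirmed by least squares on simulated data (400,000 participants, SD units).

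**Inputs.** From the documents: R7 concerns change; Step 2 contains hours, format and ACS demographics; format is chosen by the participant. Assumed, because the documents are silent:
- difference in hours, virtual minus in-person: dh = -0.5 or 0 SD
- effect of hours on the outcome: b = 0 to 0.3 SD per SD of hours
- entrance gap, virtual minus in-person: g = -0.2, 0 or +0.2 SD
- slope of follow-up on entrance score: r = 0.5
- direct effect of format, other than through hours: d = 0

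**1. Hours in the model.** The overall difference in change is D = d + b x dh. With hours held fixed, the format coefficient is d. The shift is therefore -b x dh.

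| dh | b | Overall difference D | Coefficient with hours |
|---|---|---|---|
| -0.5 | 0.1 | 0.1 x (-0.5) = -0.05 | 0.00 |
| -0.5 | 0.3 | 0.3 x (-0.5) = -0.15 | 0.00 |
| 0 | 0.3 | 0.3 x 0 = 0.00 | 0.00 |

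The zero in the last column follows from setting d = 0. The general result is the shift, which is the same for any d and is nil when hours do not differ.

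**2. An unmeasured factor behind both hours and outcome** (motivation, for instance). Let it load 0.5 on hours and 0.25 on the outcome, with within-format variance of hours equal to 1. The fitted hours slope becomes b + 0.5 x 0.25 = b + 0.125. The format coefficient becomes d - 0.125 x dh = 0 + 0.0625, about +0.06. This holds whether the true D is 0.00 (b = 0) or -0.10 (b = 0.2). In the second case the sign reverses.

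**3. Dependent variable and entrance score, hours left out.** Take D = -0.15 and let the entrance gap be a stable difference between the groups.

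| Model | Format coefficient | g = +0.2 | g = -0.2 |
|---|---|---|---|
| Change, no entrance score | D | -0.15 | -0.15 |
| 1-year index, no entrance score | D + g | +0.05 | -0.35 |
| Either outcome, with entrance score | D + (1 - r) x g | -0.05 | -0.25 |

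The first row is R7 as worded. The second absorbs the whole entrance gap. The third is a legitimate but different quantity: the difference between participants with the same entrance score.

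**The case against.** **Exploratory and non-causal.** True, and it limits the stakes. It does not make the coefficient answer R7, because the descriptive quantity itself changes once hours are held fixed.

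**A separate format analysis is announced.** The SAP mentions a moderation analysis for delivery format and lists format and dosage as distinct possible explorations, so separate models may be intended. But no such model is written down, and Step 2 lists hours and delivery dummies together for a single analysis.

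**No evidence that format affects hours.** This stands. A reader might infer that hours are a consequence of format. The documents do not say so and report no hours by format; every magnitude above is assumed. The shift needs only that mean hours differ between the groups, for whatever reason, and a model without hours answers R7 whether or not they do.

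**Open covariate wording and planned refinement of methods.** The general line on relevant co-variables could bring in the entrance score. It does not take out hours, which are expressly listed.

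**A stronger reading about the entrance score.** A reader might infer that leaving it out by itself invalidates the R7 answer, with regression to the mean producing a false difference of (1 - 0.5) x 0.2 = 0.10 SD. The documents do not support this. R7 is worded in terms of change, and a change-score model without the entrance score gives exactly that difference. Calling the 0.10 false requires the two self-selected groups to regress toward a common mean, which is contestable. The entrance score is also unnamed rather than excluded. What remains is precision: with r = 0.5 as the correlation and unit variances, residual variance is 1 - 0.5^2 = 0.75 with the entrance score against 2 x (1 - 0.5) = 1.0 for the change score.

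**Conclusion.** The concern holds in two parts. First, the only specified model that can answer R7 conditions on hours received, so its format coefficient is a difference at equal hours. The discrepancy is the hours effect times the format difference in hours: 0.05 to 0.15 SD under the assumed values, nil if hours do not differ by format, and possibly enough to reverse the sign if something unmeasured drives both attendance and outcome. The structural point rests on the text alone; the sizes rest on assumptions.

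Second, Step 2 does not define its dependent variable. If it is the 1-year index without the entrance score, the format coefficient absorbs the full entrance gap. If it is change, leaving out the entrance score does not bias R7 as worded.

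R7 is exploratory. The confirmatory questions R1 to R6 use the paired comparisons in Step 1 and are not affected. The change is worth making before the data are analysed, so that the plan answers the question it poses.

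**What to change.** Amend SAP section IV.A, Step 2:

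- Define the dependent variable for R7 as change from entrance to 1 year.
- Answer R7 from a regression of that change on delivery format and pre-enrollment (ACS) covariates, without hours.
- For the yes/no items in Protocol Table 9 (financial and job readiness), use an analogous model suited to binary data, again without hours. One option is a logistic model for repeated measures with a format-by-wave term.
- If the 1-year index is preferred as the outcome, include the entrance score and state that the result is a difference conditional on it.
- Report hours received by format, and a model that includes hours, as separate exploratory analyses labelled as such. Do not read R7 from the model with hours.

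The cost is a few sentences in the SAP and one extra regression per outcome. No new data are needed.
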